3.1 Clinical Site

The study will be performed at the University of Virginia. Screening procedures will be performed either virtually or on site, at a clinical research unit, or at the hotel.

3.2 Participant Recruitment and Enrollment

We will enroll up to 24 participants who have been diagnosed with T1D for at least one year. This enrollment number accounts for dropouts or screen failures that may occur. The goal is to complete a total of approximately 16 participants.

3.3 Informed Consent and Authorization Procedures

Before consent has been obtained, participants will be asked inclusion/exclusion criteria questions during pre-screening to determine study eligibility. Before completing any procedures or collecting any data that are not part of usual care, written informed consent will be obtained. Potential eligibility may be assessed as part of routine care examination.

A participant is considered enrolled when the informed consent forms have been signed by the participant and the study team.

Consenting procedures and documentation are defined in section 14.3.

After informed consent has been signed, a potential participant will be evaluated for study eligibility through review of medical history, performance of physical exam by a licensed health care professional, and other testing as needed per the I/E criteria.

3.4 Participant Inclusion Criteria

The participants must meet all of the following inclusion criteria in order to be eligible to participate in the study.

1. Age ≥ 18.0 years old at time of consent
2. Clinical diagnosis, based on investigator assessment, of Type 1 Diabetes for at least one year.
3. Having used an AID system equipped with Dexcom G6 or G7 CGM within the last three months (does not need to be continuous use if CGM was unavailable for instance).
4. Currently using insulin for at least six months.
5. Willingness to switch to use a commercially approved personal insulin (e.g., lispro or aspart, or biosimilar approved products) within the study pump as directed by the study team.
6. Has one or more supportive companions knowledgeable about emergency procedures for severe hypoglycemia and able to contact emergency services and study staff that either

lives with participant or located within approximately 30 minutes of participant and able to locate participant in the event of an emergency.

7. Participant not currently known to be pregnant or breastfeeding.
8. If participant capable of becoming pregnant, must agree to use a form of contraception to prevent pregnancy while a participant in the study (e.g. hormonal contraception, abstinence from heterosexual intercourse). A negative serum or urine pregnancy test will be required for all females of childbearing potential. Participants who become pregnant will be discontinued from the study. Also, participants who during the study develop and express the intention to become pregnant within the timespan of the study will be discontinued.
9. Willingness to use the study AIDANET system (CGM, pump, and phone) during the study period.
10. Willingness not to start any new non-insulin glucose-lowering agent during the course of the trial.
11. Willingness to participate in all study procedures including the house/hotel sessions.
12. Access to internet at home and willingness to upload data during the study as needed.
13. Investigator has confidence that the participant can successfully operate all study devices and is capable of adhering to the protocol.
14. Participant is proficient in reading and writing English.

3.5 Participant Exclusion Criteria

The participant must not have any exclusion criteria in order to be eligible to participate in the study.

1. Plans to start a new non-insulin glucose-lowering agent (e.g., GLP-1 receptor agonists, Symlin, DPP-4 inhibitors, sulfonylureas). Participants may be on a stable dose of such an agent for at least the past month.
2. Current use of an SGLT-2 or SGLT-1/2 inhibitor due to risk of euglycemic DKA.
3. Hemophilia or any other bleeding disorder.
4. History of severe hypoglycemic events with seizure or loss of consciousness in the last 12 months.
5. History of DKA event in the last 12 months.
6. Stage 4 chronic renal disease or currently on peritoneal or hemodialysis.
7. Currently being treated for adrenal insufficiency.
8. Currently being treated for a seizure disorder.
9. Hypothyroidism or hyperthyroidism is not adequately treated.
10. Use of oral or injectable steroids at the time of enrollment or within the last 4 weeks.
11. Planned surgery during the study period.
12. Known ongoing adhesive intolerance that is not well managed.
13. A condition, which in the opinion of the investigator or designee, would put the participant or study at risk.

14. Participation in another interventional trial at the time of enrollment.

15. Participant with a direct supervisor involved in the conduct of the trial.

3.6 Screening Procedures

The participant will be evaluated for study inclusion and exclusion eligibility after the informed consent forms have been signed by the participant and the study team. Screening procedures will last approximately 1-2 hours. The visit may occur in-person or remotely by HIPAA compliant video communication (e.g., Zoom, Webex). The following procedures may be performed/data collected/eligibility criteria checked and documented:

1. Inclusion and Exclusion criteria assessed
2. Demographics, including:
 - a. Date of birth
 - b. Gender
 - c. Race
 - d. Ethnicity
3. Medical History, including diabetes history
 - a. Duration of disease (number of years)
 - b. History of pump use
 - c. History of CGM use
 - d. Current treatment
 - e. Severe hypoglycemia history
 - f. DKA history
 - g. History of seizures
 - h. Loss of consciousness
4. Basal rates or basal insulin dosing
5. Carbohydrate ratios
6. Insulin sensitivity factors
7. Target glucose
8. Average daily insulin
9. Surgical history
10. Allergies
11. Concomitant medications
12. Physical Examination – A historical history and physical report within 6 months of screening appointments may be used but is not required for eligibility. If vitals are not available, may include self-reported values of all available vitals.
 - a. Weight
 - b. Height
 - c. Blood pressure
 - d. Temperature
 - e. Heart Rate

372 13. Screening Labs

- 373 a. Urine or serum pregnancy test for all women of childbearing potential (this test can
374 be done remotely with results sent to the study team)

375 A physical exam documented in the prior 12 months can suffice for the physical exam but will not
376 serve as an exclusion criterion if not available. Participants may self-report height, weight, blood
377 pressure, temperature, and heart rate; or these may be obtained by study staff at the enrollment
378 visit. An HbA1c value obtained in the previous one month may serve for the enrollment HbA1c
379 value.

380 If needed based on medical history, investigators may include baseline chemistry panel, liver
381 function tests, hematocrit, and thyroid stimulating hormone (lab results within one year of
382 screening appointment may be used). Any labs required may be obtained at a local laboratory (e.g.,
383 LabCorp, Quest) convenient to the participant. The study physician or physician designee will
384 have the discretion to repeat screening tests if applicable.

385 **3.7 Screen Failures / Participant Dropout**

386 If an exclusionary condition is identified, the study participant will be excluded from participation
387 with follow up and referral to their primary care physician as needed.

388 If the study participant is pregnant, the study physician will discuss the results of the blood test
389 with the participant and the participant will be asked to seek confirmation of the test and the
390 appropriate medical care.

391 Participants who screen-fail or dropout will be replaced if it occurs prior to the Hotel Admission.
392 Screen failed participants may be re-screened if their clinical situation changes as determined by
393 the study physician.

394 **3.8 Personal Equipment Downloads**

395 Up to 6 months of historical data from the participant's personal insulin pump, glucometer, or
396 continuous glucose monitor may be downloaded or recorded. Data will be obtained from the
397 participant's personal insulin pump, glucometer and CGM. This data may be obtained through the
398 commercial applications (e.g., Source, Tidepool, and Dexcom).

399 **3.9 Surveys**

400 Participants will be asked to complete the Demographic Data Survey, INSPIRE Survey, and
401 Technology Expectations Survey as described in section 8.2 prior to using AIDANET equipment.

402 **3.10 Other Considerations**

403 This study is not meant to find out if the participant has any other disease or problem. The study
404 leaders will alert the participant if any of the research results are important to the participant's
405 health during the study. The participant may have a copy of the screening tests to discuss with the
406 personal physician. If blood tests are completed, any blood left over will be thrown away. It will
407 not be stored for any future testing.

408 **3.11 Randomization**

409 Once eligibility is met and screening procedures are completed, the participant will proceed to
410 Randomization. Participants will be randomized 1:1 to one of two groups:

411 **GROUP A:** AIDANET followed by AIDANET+ BPS_RL during the hotel session

412 **GROUP B:** AIDANET+ BPS_RL followed by AIDANET during the hotel session

413 Randomization will occur via REDCap module.

Chapter 4: Study Devices & Training Visit

Visit 2

An HbA1c value for the participant will be collected prior to the start of the DiAs system. This can be a point-of-care value, lab value, or historical value from within 4 weeks of signing consent. Participants will be asked to place a new sensor 24-72 hours prior to the start of the Visit 2 to allow time for the CGM to warm-up prior to DiAs initialization. The study system is designed to enable full closed loop control and consists of the following elements: the diabetes assistant (DiAs) prototyping platform (smart phone), connected to a Tandem t:AP research insulin pump and a Dexcom G6 CGM.

Participants will come to the research center for initiation and training on the study device as described in Section 4.1. This will consist of 4-8 hours of training, tailored to the individual and include a supervised meal/snack. The participant will be asked to have an active Dexcom G6 sensor by the start of Visit 2; otherwise, a new CGM sensor will be placed. The study team will perform vital signs and inquire about any changes to the participant's medical history. Any changes to medical history will be communicated to the medical physician to ensure continued eligibility and participation.

The participant's CGM reading, and ketone concentration will be recorded. In the event that the participant's CGM reading is not between 80-250 mg/dL or ketone concentration is ≥ 0.6 mmol/L prior to initiation of the FCL system, the study physician may recommend additional insulin dosing according to the participants' usual doses. Study physician may elect to cancel participant's participation in the study if concerned about their medical safety. This participant will not be replaced.

The participant's home insulin pump will be discontinued, and the study insulin pump will be initiated. The study team will ensure the proper function of the CGM and insulin pump. The CGM used in the study is FDA-approved for the non-adjunctive measurement of blood glucose (i.e., the CGM reading can be used for insulin dosing decisions). The CGM readings will be the primary source of blood glucose values. There is no required protocol fingerstick blood glucose measurements at home other than at times of CGM calibration (if necessary) and if directed by the study team. Fingerstick blood glucose measurements may be taken whenever participants experience symptoms, if the CGM glucose is suspected to be erroneous, or any time the participant would like to be reassured. Glycemic Treatment Guidelines to be used during Visit 2 and the home portion are defined in section 6.6.

Any relevant contacts will be recorded on the CRF and summarized as appropriate (e.g. contact that is not a scheduling or supplies issue will not be recorded).

Participant will have a CGM between 80-250 mg/dL prior to leaving study site at conclusion of training session.

Remote monitoring will be in place during the At-Home Periods as detailed in section 7.2.

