INSPIRE & Technology Expectation/ Assessment Survey	X						X (post)	
Randomization	X							
AIDANET use with Remote monitoring		X	X					
AIDANET or AIDANET+ BPS_RL use					X	X		
AIDANET+ BPS_RL 1-week use with Remote monitoring							X	
Check-in visit			X				X	
Review diabetes management and AEs			X	X			X	

Contact type is Clinic Visit and Remote which includes videoconferencing, phone, text messages and emails.

TABLE 2. METRIC CAPTURE TIMELINE

	Enrollment	AIDANET At-Home	Hotel Sessions	AIDANET+ BPS_RL At-Home
Visit	1	3	5 & 6	7
Demographic Data	x			
HbA1c	x			
CGM Data		x	x	x
TIR 70-180 mg/dL		x	x	x
CGM%<54 mg/dL		x	x	x
CGM%<70 mg/dL		x	x	x
CGM%>180 mg/dL		x	x	x
CGM%>250 mg/dL		x	x	x
Mean CGM		x	x	x
Time in Automation		x	x	x
Total Daily Insulin Dose		x	x	x
Number of Boluses per Day		x	x	x
Exercise: CGM %<70 mg/dL		x	x	x
Unannounced Meals: % CGM>250 mg/dL		x	x	x

1	Table of Contents	
2	Chapter 1: Background and Introduction.....	13
3	Chapter 2: Study Synopsis	16
4	2.1 Study Objective.....	16
5	2.2 Specific Aims and Hypotheses	16
6	2.3 Study Design.....	16
7	2.4 Study Hardware/Software.....	17
8	2.5 Timing of Device Use.....	17
9	2.6 Meal Testing	18
10	2.7 Study Devices Download.....	18
11	2.8 Study System Issues.....	18
12	Chapter 3: Study Screening	19
13	3.1 Clinical Site.....	19
14	3.2 Participant Recruitment and Enrollment.....	19
15	3.3 Informed Consent and Authorization Procedures.....	19
16	3.4 Participant Inclusion Criteria	19
17	3.5 Participant Exclusion Criteria	20
18	3.6 Screening Procedures.....	21
19	3.7 Screen Failures / Participant Dropout	22
20	3.8 Personal Equipment Downloads	22
21	3.9 Surveys.....	22
22	3.10 Other Considerations	22
23	3.11 Randomization	23
24	Chapter 4: Study Devices & Training Visit	24
25	4.1 Insulin Pump and DiAs.....	25
26	4.2 Continuous Glucose Monitor.....	25
27	4.3 Blood Glucose Meter and Strips.....	26
28	4.4 Ketone Meter and Strips	27
29	4.5 Study Devices Accountability Procedures.....	27

30	Chapter 5: AIDANET At-Home Period	28
31	5.1 AIDANET use at home.....	28
32	5.2 Pre-Hotel Check-In Visit	28
33	Chapter 6: Supervised Hotel Fully Closed-Loop Period	29
34	6.1 Hotel Session	29
35	6.2 Qualifications and Role of the Staff.....	29
36	6.3 Hotel Session Check-In.....	29
37	6.4 Study Meals	30
38	6.5 Hotel Session Activities.....	30
39	6.6 Glycemic Treatment Guidelines	30
40	6.7 Hotel Session Discharge	31
41	6.8 Other Issues.....	31
42	Chapter 7: AIDANET+BPS_RL At-Home Period	32
43	7.1 AIDANET+BPS_RL use at home	32

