2.5 Timing of Device Use

Following screening and randomization, all participants will be trained on the use of the study equipment and AIDANET algorithm. Participants will be connected to a Dexcom G6 sensor and the Tandem t:AP pump, which will be connected to the DiAs platform. AIDANET will be started on DiAs, and the participants will be trained how to use the Dexcom G6 sensor (if using Dexcom G7 in their AID system), the Tandem t:AP pump, and DiAs/AIDANET (see Table 1 and Figure 1). The t:AP pump will be programmed with back up parameters determined by the study investigator(s). Once started, the participants will have their glucose values managed through use of this system during the At-Home and hotel periods.

One-Week AIDANET: All participants will collect approximately one week of AIDANET baseline data. During this period, participants will generally use AIDANET in FCL mode. The DiAs Remote Monitoring will be on, supervised by study personnel.

Hotel Session: Participants will arrive at the hotel in the afternoon (prior to dinner). Those randomized to Group A will continue to use their AIDANET system. Those randomized to Group B will be switched to the AIDANET+BPS_RL system. Because AIDANET and AIDANET+BPS_RL have identical user interfaces and only the priming bolus calculation is changed “under the hood,” no additional training will be needed.

One-Week AIDANET+ BPS_RL: Participants will continue to use the Tandem t:AP pump, DiAs platform running the AIDANET+ BPS_RL, and Dexcom G6 CGM for glucose control for 7 days/6

243 nights during this period. The DiAs Remote Monitoring will be on, supervised by study personnel.
244 At the end of this period participants will return to their usual diabetes therapy.

245 **2.6 Meal Testing**

246 During the home study, participants will be instructed to consume their usual diet and will not be
247 required to record the timing of the meals. 2.3

248 **2.7 Study Devices Download**

249 Data from the study devices will be captured in real-time by the remote monitoring server for the
250 DiAs system. In addition, study devices will be downloaded at the end of the home visits.

251 **2.8 Study System Issues**

252 If the CGM signal becomes unavailable for more than 20 minutes consecutively, closed loop will
253 not operate to automatically adjust insulin delivery. If the CGM is not connected, the system will
254 revert to the usual open loop function of the pump and deliver insulin with the pre-programmed

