5.2 Pre-Hotel Check-In Visit

Visit 4

All participants will be contacted by the study team approximately 24-48 hours prior to the hotel admission. The study team will verify the following information:

- a. Inquire about any changes to the participant's medical history
- b. Study equipment (e.g., CGM) has been initiated. A new CGM sensor will be placed approximately 24-72 hours prior to the hotel session for proper warm-up.
- c. Verify with participant that the goal CGM reading at time of arrival is less than 200 mg/dL; this may require contact with the study physician prior to arrival on the day of the study visit.
- d. Bring personal insulin and glucagon to hotel session.

Should any concerns regarding medical history, pump information, or unforeseen issues arise, the admission will be cancelled for that participant at the discretion of the investigator.

Chapter 6: Supervised Hotel Fully Closed-Loop Period

Visit 5 and 6

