6.3 Hotel Session Check-In

Participants will arrive at the hotel on the first day of the hotel session. The study team will perform vital signs and inquire about any changes to the participant's medical history. Any changes to medical history will be communicated to the medical physician to ensure continued eligibility and participation.

The participant's CGM reading, and ketone concentration will be recorded. In the event that the participant's CGM reading is not between 80-250 mg/dL or ketone concentration is ≥ 0.6 mmol/L prior to initiation of the FCL system, the study physician may recommend additional insulin dosing according to the participants' usual doses. Study physician may elect to cancel participant's participation in the hotel admission if concerned about their medical safety. This participant will not be replaced.

The participant's home insulin pump will be discontinued, and the study insulin pump will be initiated. The study team will ensure the proper function of the CGM and insulin pump. The CGM used in the study is FDA-approved for the non-adjunctive measurement of blood glucose (i.e., the CGM reading can be used for insulin dosing decisions). The CGM readings will be the primary source of blood glucose values. There is no required protocol fingerstick blood glucose measurements other than at times of CGM calibration (if necessary) and if directed by the study team. Fingerstick blood glucose measurements may be taken whenever participants experience

symptoms, if the CGM glucose is suspected to be erroneous, or any time the participant would like to be reassured. Glycemic Treatment Guidelines to be used during the hotel admission are defined in section 6.6.

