12.1 Design and Randomization

This pilot study aims to demonstrate the safety and feasibility of the AIDANET+BPS_RL algorithm, which replaces with a new BPS_RL the bolus priming module of our AIDANET system described in IDE #G240236, which was approved by the FDA on October 10, 2024.

As presented in Figure 1, this study is a randomized cross-over trial comparing AIDANET to AIDANET+BPS_RL, which includes the new BPS_RL. A week of AIDANET control at home will be followed by a two-night hotel stay where participants will cross over from AIDANET to AIDANET+BPS_RL and vice versa and will learn how to operate the new BPS_RL for a subsequent AIDANET+BPS_RL week at home. The participants are not expected or encouraged to announce meals to the system, thus the system will run in fully-automated closed loop (FCL) mode.

Eligible participants will be randomized to two groups, A and B, which differ only by the order of administration of AIDANET or AIDANET+BPS_RL during the hotel section of the study. The remaining procedures are identical for both groups A and B. The randomization list will use a sequence of computer-generated pseudorandom Bernoulli trials and will aim to balance groups by baseline HbA1c (Figure 1).

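### Sequence is assigned about 10 days before it takes effect, with discretionary exits in between, and the plan does not say it is withheld until admission is decided

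*Combined protocol and SAP*

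**What the plan says.** **Timing.** Section 3.11 reads "Once eligibility is met and screening procedures are completed, the participant will proceed to" randomisation, Table 1 marks randomisation in the Visit 1 (Day 1) column, and 2.5 gives the same order of steps: "Following screening and randomization, all participants will be trained on the use of the study equipment and AIDANET algorithm". Table 1 puts the hotel sessions on Days 11-13.

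**What the sequence changes.** According to 12.1 the groups "differ only by the order of administration of AIDANET or AIDANET+BPS_RL during the hotel section of the study", and the "remaining procedures are identical for both groups A and B".

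**Exits after randomisation.**
- Visit 2 (Chapter 4): the study physician may cancel participation on safety grounds. That person is not replaced.
- Visit 4 (5.2): if concerns arise, "the admission will be cancelled for that participant at the discretion of the investigator". Replacement is not mentioned.
- Visit 5 (6.3): "Study physician may elect to cancel participant's participation in the hotel admission if concerned about their medical safety". That person is not replaced.

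**General replacement rule.** Section 3.7: "Participants who screen-fail or dropout will be replaced if it occurs prior to the Hotel Admission".

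**Who knows the sequence.** Section 3.11 names a REDCap module, and 12.1 describes Bernoulli trials with an aim to balance on baseline HbA1c. Neither says who sees the assignment or when. Section 2.5 has Group B switched to the new algorithm on arrival at the hotel, so someone must know by then.

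**The concern.** In a crossover, the decision to let someone enter should not be able to depend on the order that person has drawn. Here the order exists well before that decision, and nothing in the plan prevents the people deciding from knowing it. A participant who arrives with unsettled glucose might be cancelled more readily if the new algorithm is due that night (Group B) than if the familiar one is (Group A).

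If so, Group B would enter its first session in a better passing state than Group A. That favours AIDANET+BPS_RL in Group B's comparison without an equal and opposite effect in Group A. Period adjustment cannot remove this, because the selection differs by sequence. It matters because the first success criterion in 12.6 is only that mean TIR is higher on the new system, whatever the p-value, with about 16 completers.

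The early assignment buys nothing. Training and the first home week are the same for both groups, and 2.5 says that no further training is needed to switch algorithms.

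**Working it through.** **1. Lead time.** Table 1: Day 11 − Day 1 = 10 days.

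**2. Replacement statements side by side.** Section 3.7 replaces dropouts before hotel admission. Chapter 4 (Visit 2) and 6.3 (check-in) say the cancelled participant is not replaced, and 5.2 (Visit 4) is silent. A Visit 2 cancellation happens before admission, so 3.7 and Chapter 4 can be read to conflict. None of these sections says which sequence a replacement receives.

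**3. Model for sequence-dependent cancellation** (assumed; the plan gives no variance or cancellation rates). Session errors e1 and e2 are independent with SD 1, so the paired difference has SD √2. There is no true effect. The estimate is (mean difference in A + mean difference in B)/2, which removes any common period effect. With 8 completers per group its standard error is 1/√16 = 0.25 SD of the paired difference. A pre-hotel score correlates r1 with e1 and r2 with e2. Nobody is cancelled in Group A (8 of 8 complete); the 2 worst of 10 are cancelled in Group B.

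- The expected two lowest of 10 standard normal values are −1.539 and −1.001, so the 8 retained average (1.539 + 1.001)/8 = 0.3175.
- Bias = (r1 − r2) × 0.3175/(2√2) = 0.112 × (r1 − r2) SD of the paired difference.
- Chance of a positive estimate = Φ(bias/0.25).

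| r1 | r2 | Bias (SD) | Chance of positive estimate |
|---|---|---|---|
| 0.2 | 0 | 0.022 | 54% |
| 0.4 | 0 | 0.045 | 57% |
| 0.6 | 0 | 0.067 | 61% |
| 0.4 | 0.2 | 0.022 | 54% |
| 0.4 | 0.3 | 0.011 | 52% |
| 0.4 | 0.4 | 0 | 50% |

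Simulation with 200,000 runs per row agrees within simulation error.

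**4. Cancellation in both groups** (r1 = 0.4, r2 = 0). If the worst 1 of 9 in Group A is also cancelled, the retained mean there is 1.485/8 = 0.186. The bias is 0.4 × (0.3175 − 0.186)/(2√2) = 0.019 SD, and the chance of a positive estimate is 53%. If the worst 2 of 10 are cancelled in both groups, the bias is zero.

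**5. Selection on stable control.** This cancels within person once period is adjusted for. In a simulation with an assumed effect of 4 points, a period effect of 5 points and 70% of poorly controlled Group B participants cancelled and replaced, the period-adjusted estimate was 4.01. The unadjusted one was 4.63. The mean split was about 8.97 to 7.03, which passes (8.97 − 7.03)/16 × 5 = 0.61 points of the period effect through. Section 12.4 stresses the crossover interaction, most naturally read as the period-adjusted contrast, but does not name a period term.

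**6. Scale against the plan's target.** Section 12.2 aims for f = 0.2 and N = 50 in the later trial. With dz = 2f/√(2(1 − ρ)) and assumed ρ = 0.5, dz = 0.4. At assumed two-sided 5% and 80% power, N = ((1.960 + 0.842)/0.4)² = 49.1, so 50, which matches the plan. A bias of 0.022 to 0.067 SD is then 6% to 17% of the target effect. At ρ = 0 (dz = 0.283) it is 8% to 24%; at ρ = 0.7 (dz = 0.516), 4% to 13%.

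**The case against.** The strongest reply is that no allocation failure has been shown, and that much is right. A reader might infer that the assignment is open from Day 1, or that concealment is broken. The documents do not say so. Assignment follows eligibility, Bernoulli draws are hard to predict, and a REDCap module can hold a result back. The supportable statement is only that the plan does not say the sequence is withheld until entry to the crossover is decided.

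Two other readings also go too far:
- **Cancelled participants are routinely replaced.** At Visit 2 and at check-in they expressly are not.
- **The whole enrolment allowance (24 − 16 = 8 in 3.2, or 20 − 15 = 5 in 12.2) is loss after randomisation.** Section 3.2 says its allowance includes screen failures, and those found at screening are never randomised.

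The motive can be doubted too. Both groups receive the new algorithm at the hotel, Group A one night later under the same supervision, and everyone then takes it home. No section links any exit to sequence. The two sessions also fall within about 40 hours, so a poor state on arrival may affect both and largely cancel.

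These points limit the size of the problem, but they do not remove it. Check-in acts on that afternoon's CGM and ketones, and the first 18-hour window opens at 6 PM, so a passing state could weigh more on the first session than the second. The plan gives no reason for assigning early.

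**Conclusion.** The concern stands as a modest weakness of design that is easily removed. The sequence is fixed about 10 days before it is needed, discretionary exits fall in between, and the plan is silent on withholding it. The possible bias of about 0.02 to 0.07 SD of the paired difference is an illustrative upper range. It requires cancellations only in Group B and a pre-hotel state that affects the first session but not the second, and it shrinks to zero as either condition is relaxed. Even the top value is about a quarter of the standard error (0.067/0.25 = 0.27).

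A reader might also infer that later randomisation would even out the sequence groups. It would not: pure Bernoulli assignment of 16 people gives a 10:6 split or worse with probability 45%, whenever it is done. Unequal group sizes alone do not bias a period-adjusted estimate. The case for the change rests on sequence-dependent exclusion, not on balance of numbers.

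**What to change.** - **Move the step.** Run the existing REDCap randomisation at hotel check-in (Visit 5), after the admission checks and the decision to admit, and immediately before the device is set to AIDANET or AIDANET+BPS_RL. Move the Table 1 mark from Visit 1 to Visit 5 and edit 2.5 and 3.11 to match.
- **Reconcile replacement.** Make 3.7, Chapter 4, 5.2 and 6.3 agree on who is replaced. Once randomisation follows admission, replacing a pre-hotel loss no longer touches the allocation, and the question of which sequence a replacement receives disappears.
- **Report.** Give the number lost before randomisation, and any later cancellation by sequence. Section 12.8 describes all randomised participants, so its table would then cover those admitted.

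There is a side benefit. Table 1 collects HbA1c at Visit 2, after the current randomisation, although 8.1.1 places it at screening. Under either timing it would be available for the balancing in 12.1.

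The cost is protocol wording, one table cell and the timing of one REDCap step. The small downside is that staff learn the sequence only on the day of admission.
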